Attachment 2: Anticipated Events**Anticipated Event**

An anticipated event is an AE (serious or non-serious) that commonly occurs as a consequence of the underlying disease or condition under investigation (disease related) or background regimen.

For the purposes of this study the following events will be considered anticipated events:

- Pneumonia
- Bronchitis
- Sinus infection
- Ear infection
- Worsening of asthma, asthma attack
- Chronic obstructive pulmonary disease exacerbation
- Complications of sickle cell disease, sickle cell crisis
- Complications of diabetes mellitus, diabetic ketoacidosis
- Acute respiratory distress syndrome

Reporting of Anticipated Events

These events will be captured on the eCRF and in the database, and will be reported to the sponsor as described in Section 12.3.1, All Adverse Events. Any event that meets SAE criteria will be reported to the sponsor within the appropriate timeline as described in Section 12.3.2, Serious Adverse Events. These anticipated events are exempt from expedited reporting as individual single cases to Health Authorities. However, if based on an aggregate review, it is determined that an anticipated event is possibly related to study drug, the sponsor will report these events in an expedited manner.

Anticipated Event Review Committee (ARC)

In this study, the IDMC will perform the role of an Anticipated Event Review Committee (ARC) and will conduct reviews of pre-specified anticipated events at an aggregate level. The IDMC will provide the recommendation to the Sponsor Committee as to whether there is a reasonable possibility that an anticipated event is related to the study drug.

Statistical Analysis

Details of statistical analysis of anticipated events, including the frequency of review and threshold to trigger an aggregate analysis of anticipated events will be provided in a separate Anticipated Events Safety Monitoring Plan.

Attachment 3: Taste/Swallowability Questionnaire

The taste and swallowability questionnaire should be completed within approximately 15 minutes after the first and last intake of the study drug (consequently, the questionnaire should be completed 2 times in total by the subject).

Date (DD/MM/YYYY): _____

Subject Clinical Trial ID number: _____

Questionnaire completion time (24-hours format → insert a time between 00:00 and 23:59):
_____:_____

Questions:**1. How did you take the study drug? (Put a cross in the box beneath your appreciation)**

A. I swallowed the tablets whole	B. The tablets were dispersed in water (only applicable at the hospital)

If you have answered A, please answer the following questions:

2. Taste (Put a cross in the box beneath your appreciation)**Sweetness**

None	Weak	Moderate	Strong

Bitterness

None	Weak	Moderate	Strong

Flavour

None	Weak	Moderate	Strong

Overall

None	Weak	Moderate	Strong

3. Swallowability:

On a scale of 1-7, how difficult/easy was it to swallow the tablet? (Circle the number corresponding to your appreciation)

1. Very difficult
2. Moderately difficult
3. Slightly difficult
4. Neither difficult nor easy
5. Slightly easy
6. Moderately easy
7. Very easy

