- The acceptability of the pimodivir formulation in adolescents, as measured by a taste and swallowability questionnaire.

Exploratory Endpoint

- A patient-reported outcome (PRO) based on subjects' ratings on the influenza symptom diary will be formulated.

Refer to Section 9, Study Evaluations, for evaluations related to endpoints.

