3. STUDY DESIGN AND RATIONALE

3.1. Overview of Study Design

This is a Phase 3 randomized, double-blind, placebo-controlled, multicenter study to evaluate the efficacy and safety of pimodivir in combination with SOC treatment vs placebo in combination with SOC treatment in adolescent (13 to 17 years), adult (18 to 65 years), and elderly (>65 to ≤85 years) hospitalized subjects with influenza A infection. A target of 600 hospitalized influenza-infected subjects will be randomly enrolled in this study with 300 subjects planned per treatment arm. The aim is to enroll a minimum of 60 adolescent subjects in this study in selected countries and study sites consistent with local regulations. The randomization will be stratified for baseline NEWS2 (4-5 or >5), type of baseline SOC (including or not including influenza antiviral treatment), and time since onset of influenza symptoms (first administration of study drug within 72 hours or between 72 and 96 hours since onset of influenza symptoms). The study population should consist of at least 75% of subjects (75% of the total planned sample size of 600 subjects) with first administration of study drug ≤72 hours since onset of influenza symptoms.

Subjects who meet all eligibility criteria will be randomized in a 1:1 ratio to receive 1 of the following treatments.

- Treatment Arm 1: pimodivir 600 mg bid for 5 days + SOC treatment*
- Treatment Arm 2: pimodivir placebo bid for 5 days + SOC treatment*

*SOC treatment is determined by the investigator based on local practice, and may include influenza antivirals and/or supportive care only. The choice to use influenza antivirals as part of the SOC should be made before randomization. The influenza antiviral should be started no later than the day of first study drug intake. An influenza antiviral as part of the SOC cannot be changed (eg, switching one influenza antiviral for another) during either the treatment period or extension phase, with the exception that an influenza antiviral may be discontinued in the case of a suspected AE.

Study drugs will be taken orally. During hospitalization, in case of medical need, study drug tablets may be dispersed in water before intake (in case of administration via a nasogastric tube or if the subject has difficulties swallowing the tablets). Refer to the pharmacy manual/study site investigational product manual for additional guidance on study drug preparation, handling, and storage.

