11.10. Taste and Swallowability

Taste and swallowability questionnaire results (collected for adolescents who take pimodivir or placebo tablets; not applicable when tablets are administered via nasogastric tube) will be summarized per tablet intake (first and last intake of the study drug) by means of frequency tabulations. For overall taste, a dichotomization will be made for the overall question, categorizing ‘bad’ and ‘almost acceptable’ vs ‘acceptable’ and ‘good’. For swallowability, a dichotomization will be made of ‘slightly difficult’ or worse vs ‘neither difficult nor easy’ or better. The number of subjects (%) will be presented by category.

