6. TASTE AND SWALLOWABILITY

6.1. Definition

Taste and swallowability will only be assessed for adolescents in this study.

The acceptability of the taste will be derived from the responses to the overall question on taste, dichotomizing the responses 'None' and 'Weak' as acceptable and responses 'Moderate' or 'Strong' as unacceptable.

For swallowability, a dichotomization of the responses will be made of 'slightly difficult' or worse vs 'neither difficult nor easy' or better.

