6.2. Analysis Methods

Taste and swallowability questionnaire results (collected for adolescents only who take pimodivir or placebo tablets; not applicable when tablets are administered via nasogastric tube) will be summarized per tablet intake (first and last intake of the study drug) by means of frequency tabulations of the actual responses. Additionally the number of subjects (%) will be presented by response category (including dichotomization) for swallowability and taste separately. Analyses will be done on the safety set.

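### The adolescent form asks taste and swallowability only of those who swallowed the tablets whole, although the protocol and SAP exempt only nasogastric administration

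*Protocol*

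**What the plan says.** Protocol 2.1.2 lists as a secondary endpoint "The acceptability of the pimodivir formulation in adolescents, as measured by a taste and swallowability questionnaire". The instrument is Attachment 3, completed after the first and the last intake.

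- **The form.** Question 1 has two answers: A, swallowed whole, and "B. The tablets were dispersed in water (only applicable at the hospital"). The line after it is "If you have answered A, please answer the following questions". The taste items (question 2) and the seven-point swallowability item (question 3, "how difficult/easy was it to swallow the tablet") follow. Nothing is provided for B.
- **When dispersion is allowed.** Protocol 3.1, repeated in the Section 6 footnotes, allows it during hospitalization for medical need: "in case of administration via a nasogastric tube or if the subject has difficulties swallowing the tablets".
- **Who is exempt.** Protocol 11.10 says the questionnaire is "not applicable when tablets are administered via nasogastric tube". Protocol 9.1.3 and 9.5 and SAP 6.2 carry the same exemption and no other.
- **The analysis.** SAP 6.1 states: "For swallowability, a dichotomization of the responses will be made of" difficult ratings against neutral or easy ones. It derives taste acceptability from the overall taste item. SAP 6.2 adds: "Additionally the number of subjects (%) will be presented by response category (including dichotomization) for swallowability and taste separately". Neither section places answer B in a class or sets a denominator for it.

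**The concern.** The procedure and analysis text treats an adolescent who drinks the dispersed tablets as someone to be assessed. The form does not assess that adolescent. By the protocol's own rule, oral dispersion is for subjects who have trouble swallowing the tablets, so for oral intake answer B is tied to the very problem that question 3 measures. Those subjects drop out of the swallowability percentage, and no taste information is collected on the dispersed form.

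At stake is what the acceptability endpoint can be said to describe. A reader of the study report would take the swallowability percentage as a statement about adolescents given this formulation. It would be a statement about those who managed the tablets whole.

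**Working it through.** The plan states no figure on this point, so there is none to reproduce. The check is a comparison of passages, followed by an illustration on assumed inputs.

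**1. Follow each mode of intake through form and plan.**

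| Mode of intake | Exempt under Protocol 9.1.3, 9.5, 11.10 and SAP 6.2? | Taste asked in Attachment 3? | Swallowability asked? | Class in SAP 6.1 |
|---|---|---|---|---|
| Whole (A) | No | Yes | Yes | Yes |
| Dispersed, by mouth (B) | No | No | No | None |
| Dispersed, nasogastric (B, if the form is completed) | Yes | No | No | None |

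The second row is the conflict. The form also cannot tell the second row from the third, because B records neither route nor reason.

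**2. Direction of the effect on swallowability.** Take all adolescents with an oral intake. Let *q* be the share of whole-tablet swallowers rating the tablet as slightly difficult or worse. Let *d* be the share of oral takers who used dispersion because of swallowing difficulty. Assume no other oral dispersion, since Protocol 3.1 names no other reason for it.

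- Percentage as the form and SAP produce it: *q*, whatever *d* is.
- Percentage over all oral takers, with those *d* counted as having difficulty: *d* + *q*(1 − *d*).
- Difference: *d*(1 − *q*). It is zero if *d* = 0 and positive if *d* > 0 and *q* < 1.

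**3. Illustration.** The base of 60 is the minimum number of adolescents aimed for in Protocol 3.1. Both *q* (20% or 10%) and *d* (5% to 40%) are assumptions; the documents give neither.

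| *d* | Dispersed, of 60 | *q* = 20% | *q* = 10% |
|---|---|---|---|
| 5% | 3 | (3 + 0.2×57)/60 = 24% | (3 + 0.1×57)/60 = 14.5% |
| 10% | 6 | (6 + 0.2×54)/60 = 28% | (6 + 0.1×54)/60 = 19% |
| 20% | 12 | (12 + 0.2×48)/60 = 36% | (12 + 0.1×48)/60 = 28% |
| 30% | 18 | (18 + 0.2×42)/60 = 44% | (18 + 0.1×42)/60 = 37% |
| 40% | 24 | (24 + 0.2×36)/60 = 52% | (24 + 0.1×36)/60 = 46% |

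The reported figure stays at 20% or 10% in every row. The gap runs from 4 to 32 points for *q* = 20% and from 4.5 to 36 points for *q* = 10%. The width of that range shows that the documents do not fix the size.

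**4. First against last intake.** SAP 6.2 summarizes each intake separately. An adolescent who takes dispersed tablets at the first intake and whole tablets at the last is rated only at the last, so the two percentages can rest on different adolescents.

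**The case against.** The strongest reply is that the skip is logical for question 3: someone who did not swallow a tablet cannot rate swallowing it. That stands. A result conditional on whole-tablet intake is a legitimate, narrower quantity. It needs to be labelled as such, with the number left out shown beside it. The argument does not extend to taste, where a person who drank the dispersion could answer.

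It can also be said that nobody is hidden. Question 1 records B, and SAP 6.2 tabulates actual responses, so the count can be shown. That stands too, but no rule carries the count into the swallowability summary or its denominator, and B mixes oral with nasogastric use.

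Exclusion criterion 12 gives inability to swallow tablets outside the hospital as an example, which probably shrinks the group. It does not empty it, because dispersion in hospital remains allowed.

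Three stronger readings are tempting, and the documents do not support them.

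- A reader might infer that taste is asked only where nothing is tasted. Whole-tablet takers are asked about sweetness, bitterness, flavour and overall taste, and may well taste something. What is missing is the taste of the dispersed form.
- A reader might infer that the reported difficulty rate is bound to be too low, by an amount such as 9 or 27 points. That requires at least one adolescent to have used oral dispersion for swallowing difficulty, and every figure for the amount rests on assumed inputs.
- A reader might conclude that B should simply be recoded as difficult. The form records neither route nor reason, and in acutely ill inpatients trouble swallowing may reflect the illness rather than the tablet. Recoding would assign a rating the subject never gave.

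**Conclusion.** The form and the plan conflict. Adolescents who drink the dispersed tablets are not exempt under the protocol or the SAP, yet Attachment 3 asks them nothing after question 1. The swallowability percentage therefore describes whole-tablet swallowers only. It understates difficulty among all oral takers if any of them used dispersion because of swallowing difficulty; if none did, swallowability is unaffected. The size cannot be derived from the documents.

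The impact is minor. The endpoint is summarized by frequency tables in adolescents only. It is not among the seven endpoints of the confirmatory strategy in Protocol 11.4 and SAP 5.1.1, and no test in that strategy depends on it.

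**What to change.** **Attachment 3.** Split answer B into dispersed by mouth and given by nasogastric tube. For dispersion by mouth, add a yes/no item on whether it was because of difficulty swallowing the tablets. Ask the taste items after A and after dispersion by mouth. Leave question 3 for A only.

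**SAP 6.1 and 6.2.** Report taste by mode of intake. At each intake, report beside the swallowability result the number and percentage who took the tablets dispersed by mouth, and the number and percentage who did so for swallowing difficulty, with all adolescents with an oral intake as denominator. Label the seven-point dichotomy as whole-tablet swallowers. A version counting oral dispersion for swallowing difficulty as difficult may be added as a supplementary summary.

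**Cost.** The form needs one answer option, one item and a changed skip line, with the matching eCRF fields, because Protocol 9.5 has the paper form transcribed. As an attachment to the protocol it would go through an amendment. The SAP needs a few sentences and one extra table row per intake. If the form can no longer change, the SAP part still helps: show the count of B at each intake, state that it cannot be split by route or reason, and apply the whole-tablet label to both the taste and the swallowability results.

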Attachment 4: Cardiovascular Safety – Abnormalities**ECG**

All important abnormalities from the ECG readings will be listed.

Abnormality Code	ECG parameter			
	HR	PR	QRS	QT _{corrected}
Abnormalities on actual values				
Abnormally low	<45 bpm	<110 ms	-	-
Abnormally high	≥120 bpm	>220 ms	≥120 ms	-
Borderline prolonged QT (males)	-	-	-	450 ms <QTc ≤480 ms
Borderline prolonged QT (females)	-	-	-	470 ms <QTc ≤480 ms
Prolonged QT	-	-	-	480 ms <QTc ≤500 ms
Pathologically prolonged QT	-	-	-	QTc > 500 ms
Abnormalities on changes from baseline (ΔQTc)				
Normal QTc change	-	-	-	ΔQTc <30 ms
Borderline QTc change	-	-	-	30 ms ≤ΔQTc ≤60 ms
Abnormally high QTc change	-	-	-	ΔQTc >60 ms

For absolute QTc parameters the categories are defined based on the ICH E14 Guidance...^a

Vital Signs^b

The following abnormalities will be defined for vital signs:

Abnormality Code	Vital Signs parameter		
	Pulse	DBP	SBP
Abnormalities on actual values			
Abnormally low	<45 bpm	≤ 50 mmHg	≤ 90 mmHg
Grade 1 or mild	-	>90 mmHg - <100 mmHg	>140 mmHg - <160 mmHg
Grade 2 or moderate	-	≥100 mmHg - <110 mmHg	≥160 mmHg - <180 mmHg
Grade 3 or severe	-	≥110 mmHg	≥180 mmHg
Abnormally high	≥120 bpm	-	-

^a The clinical evaluation of QT/QTc interval prolongation and proarrhythmic potential for non-antiarrhythmic drugs CHMP/ICH/2/04, May 2005.

^b The classification of AEs related to hypotension and hypertension will be done according to the WHO grading scale (see also [Attachment 1](#)).

Attachment 5: National Early Warning Score (NEWS) 2: Scoring System**Chart 1: The NEWS scoring system**

Physiological parameter	Score						
	3	2	1	0	1	2	3
Respiration rate (per minute)	≤8		9–11	12–20		21–24	≥25
SpO ₂ Scale 1 (%)	≤91	92–93	94–95	≥96			
SpO ₂ Scale 2 (%)	≤83	84–85	86–87	88–92 ≥93 on air	93–94 on oxygen	95–96 on oxygen	≥97 on oxygen
Air or oxygen?		Oxygen		Air			
Systolic blood pressure (mmHg)	≤90	91–100	101–110	111–219			≥220
Pulse (per minute)	≤40		41–50	51–90	91–110	111–130	≥131
Consciousness				Alert			CVPU
Temperature (°C)	≤35.0		35.1–36.0	36.1–38.0	38.1–39.0	≥39.1	

Level of consciousness is assessed using the Alert New confusion Voice Pain Unresponsive (ACVPU) scale, which assesses five possible outcomes to measure and record a patient's level of consciousness. The assessment is done in sequence and only one outcome is recorded. For example, if the patient responds to voice, it is not necessary to assess the response to pain.

- Alert (A): a fully awake patient. Such patients will have spontaneous opening of the eyes, will respond to voice and will have motor function.
- New confusion (C): A patient may be alert but confused or disorientated. It is not always possible to determine whether the confusion is 'new' when a patient presents acutely ill. Such a presentation should always be considered to be 'new' until confirmed to be otherwise. New-onset or worsening confusion, delirium or any other altered mentation should always prompt concern about potentially serious underlying causes and warrants urgent clinical evaluation.
- Voice (V): the patient makes some kind of response when you talk to them, which could be in any of the three component measures of eyes, voice or motor – eg patient's eyes open on being asked, 'Are you okay?'. The response could be as little as a grunt, moan, or slight movement of a limb when prompted by voice.
- Pain (P): the patient makes a response to a pain stimulus. A patient who is not alert and who has not responded to voice (hence having the test performed on them) is likely to exhibit only withdrawal from pain, or even involuntary flexion or extension of the limbs from the pain stimulus. The person undertaking the assessment should always exercise care and be suitably trained when using a pain stimulus as a method of assessing levels of consciousness.
- Unresponsive (U): this is also commonly referred to as 'unconscious'. This outcome is recorded if the patient does not give any eye, voice or motor response to voice or pain.

Each of the physiological parameters and the supplemental use of oxygen should be allocated a score reflecting the magnitude of disturbance/use of supplemental oxygen. The individual scores should then be combined to derive the aggregate NEWS2 for the patient.

For more information, see reference¹³.

Attachment 6: Influenza Symptom Diary***Instructions to the Subject***

This diary consists of several questions about your flu symptoms. For each question, choose the one number that best describes the symptom at its worst severity in the past 12 hours. If you did not have the symptom in the past 12 hours, select '0' "No symptom".

1. Please select the number that describes your **cough at its worst** in the past 12 hours.

|_____|_____|_____|_____|_____|_____|_____|_____|_____|_____|

0 1 2 3 4 5 6 7 8 9 10

No
Cough

Cough as bad as
you can imagine

2. Please select the number that describes your **trouble breathing at its worst** in the past 12 hours.

|_____|_____|_____|_____|_____|_____|_____|_____|_____|_____|

0 1 2 3 4 5 6 7 8 9 10

No
Trouble Breathing

Trouble breathing as bad
as you can imagine

3. Please select the number that describes your **body aches at their worst** in the past 12 hours.

|_____|_____|_____|_____|_____|_____|_____|_____|_____|_____|

0 1 2 3 4 5 6 7 8 9 10

No
Body Aches

Body aches as bad
as you can imagine

4. Please select the number that describes your **fatigue (tiredness, weariness) at its worst** in the past 12 hours.

|_| |_| |_| |_| |_| |_| |_| |_| |_| |_| |_|

0 1 2 3 4 5 6 7 8 9 10

No
Fatigue

Fatigue as bad
as you can imagine

5. Please select the number that describes your **headache at its worst** in the past 12 hours.

|_| |_| |_| |_| |_| |_| |_| |_| |_| |_| |_|

0 1 2 3 4 5 6 7 8 9 10

No
Headache

Headache as bad
as you can imagine

6. Please select the number that describes your **sweating at its worst** in the past 12 hours.

|_| |_| |_| |_| |_| |_| |_| |_| |_| |_| |_|

0 1 2 3 4 5 6 7 8 9 10

No
Sweating

Sweating as bad
as you can imagine

7. Please select the number that describes your **nasal congestion at its worst** in the past 12 hours.

|_| |_| |_| |_| |_| |_| |_| |_| |_| |_| |_|

0 1 2 3 4 5 6 7 8 9 10

No
Nasal Congestion

Nasal congestion as bad
as you can imagine

8. Please select the number that describes your **sore throat at its worst** in the past 12 hours.

|_____|_____|_____|_____|_____|_____|_____|_____|_____|_____|

0 1 2 3 4 5 6 7 8 9 10

No
Sore Throat

Sore throat as bad
as you can imagine

9. Please select the number that describes your **chills at their worst** in the past 12 hours.

|_____|_____|_____|_____|_____|_____|_____|_____|_____|_____|

0 1 2 3 4 5 6 7 8 9 10

No
Chills

Chills as bad
as you can imagine

The overall reason for the amendment: The overall reason for the amendment is to make general updates to the text including minor grammatical, formatting, or spelling changes throughout the SAP for clarification purposes and to align with protocol amendment 2. A new section is added: to include analysis of pharmacokinetic parameters and pharmacodynamic analyses. Three new subgroups were added namely influenza season, study period (before interim, after interim) and COVID-19 impacted (Yes/No). To assess the impact of COVID-19, several tables and listings are added presenting the COVID-19 impacted subjects separately. Two new secondary endpoints based on a clinically relevant change from baseline in EQ-5D VAS are included. A new endpoint related to the HRS is added: the fundamental hospital recovery scale, reflecting the actual location/situation, which will be analysed each day from Day 2 to 14. Additionally, the following four new secondary endpoints were also added: time to NEWS2 ≤ 2 , time to clinical improvement, time to clinical failure and incidence of mortality per day.

The table below gives an overview of the changes in all applicable sections

Summary of changes: An additional analysis set was defined for the analysis of the primary endpoint and the six most important secondary endpoints. Additional analysis sets were defined for the pharmacodynamic analyses and the analysis of pharmacokinetics parameters. The criterion: “Subjects did not switch to another influenza antiviral as a part of the SOC during the treatment period” was added and the criterion: “subjects that did not use a concomitant medication that may have affected the efficacy of the study drug” was removed from the definition of the per protocol analysis set. The in- and exclusion criteria needed to define the per protocol analysis set are updated and added.

